4.5.1. Extent of Exposure

Not applicable.

4.5.2. Adverse Events/Serious Adverse Events

Adverse events analyses including the analysis of adverse events (AEs), serious adverse events (SAEs) will be based on GSK Core Data Standards. Adverse events will be coded using the standard Medical Dictionary for Regulatory Affairs (MedDRA dictionary) and grouped by system organ class (SOC). Adverse events will be graded by the investigator according to the National Cancer Institute Common Terminology Criteria for Adverse Events (NCI-CTCAE v5.0).

An overview summary of AEs, including counts and percentages of participants with any AE will be created by SOC and PT.

All SAEs will be tabulated based on the number and percentage of participants who experienced the event by SOC and PT. The summary of all SAEs will be created by SOC and PT.

A summary of fatal SAEs will also be provided.

A Summary of Fatal AEs and Non-serious AEs by SOC and PT will also be provided.

A listing of all AEs collected will be provided. SAE flags are included in the listing of all AEs. Separate supportive listings with participant level details will be generated for

- Fatal SAEs
- Non-Fatal SAEs.

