HLA genotyping		X (5)			 For participants with archived tumor specimen: Imaging by CT/MRI conducted for tumor assessment within ±4 weeks of
Liquid biopsy (blood)		X(6)		Х	tumor biopsy will be collected. Images from image-guided biopsy procedures (if conducted) will also be collected. See Section 7.2.
Genetics sample		X (7)			10. CT/MRI to assess tumor(s). Imaging visit window ±4 weeks (28 days), or -4 weeks if fresh tissue biopsy is conducted at Visit 2. Imaging for standard of care tumor assessment may be used if it
Tumor specimen		X (8)			was acquired within 28 days and conforms to the protocol imaging requirements in Section 7.2.3. Images from image-guided biopsy procedures (if conducted) will be collected.
Pre-study scans related to archived tumor specimen	X(9)				 Following completion of informed consent, patients will be provided credentials to log into the Gather Share Know Participant hub (see Section 7.1)
		N ((0)			12. For those participants who are not eligible for a GSK clinical trial, please refer to Table 2 SoA
Tumor Imaging		X (10)			 SAEs assessed as related to study procedure(s) or lead to study withdrawal
Review of AEs and SAEs that are related to study procedure(s) or lead to study withdrawal ⁽¹³⁾	Х	X	Х	x	14. Blood Pressure, Pulse Rate, Temperature. If Visit 1 and 2 are combined, vital signs only need to be recorded once.
to olday withdrawar					15. Must be signed before any study specific assessments are
Gather Share Know Credentials	X (11)				performed. 16. ECG to be performed at baseline during Visit 1 and result to be
Referral to intended GSK Treatment					entered into eCRF. An ECG done within 2 weeks of Visit 1 is
protocol			X (12)		acceptable, if the patient has not had any cardiac event.17. Withdrawal Visit applicable only if participant withdraws from study prior to Visit 3.
Review of actionable results			X		18. Visit 2 haematology and coagulation laboratory tests to be performed as close as possible to the biopsy assessment.

Table 2 Schedule of Activities For Participants Ineligible for Treatment Trial

Note: For those participants not eligible for a GSK treatment trial or other clinical trial, and who receive Standard of Care (SoC), disease will continue to be monitored under MDCI following Table 2 assessments:

CONFIDENTIAL

Procedures	Q26W until W104	Withdrawal/At Progression		
Visit Window	±4W	±4W		
Liquid Biopsy	Х	Х	Footnotes:	

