7.5.6. Death Events

For all deaths, whether or not they are considered SAEs, specific Death sections of the CRF will be required to be completed.

The Death CRF is provided immediately after the occurrence or outcome of death is reported. Initial and follow-up reports regarding death must be completed within one week of when the death is reported.

213299 Protocol Amd 03

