9.3.2. Definition of SAE

If an event is not an AE per definition above, then it cannot be an SAE even if serious conditions are met (e.g., hospitalization for signs/symptoms of the disease under study, death due to progression of disease).

An SAE is defined as any untoward medical occurrence that, at any dose, meets one or more of the criteria listed:

- o Results in death
- o Is life-threatening

The term 'life-threatening' in the definition of 'serious' refers to an event in which the participant was at risk of death at the time of the event. It does not refer to an event, which hypothetically might have caused death, if it were more severe.

Requires inpatient hospitalization or prolongation of existing hospitalization

- In general, hospitalization signifies that the participant has been detained (usually involving at least an overnight stay) at the hospital or emergency ward for observation and/or treatment that would not have been appropriate in the physician's office or outpatient setting. Complications that occur during hospitalization are AE. If a complication prolongs hospitalization or fulfills any other serious criteria, the event is serious. When in doubt as to whether "hospitalization" occurred or was necessary, the AE should be considered serious.
- Hospitalization for elective treatment of a pre-existing condition that did not worsen from baseline is not considered an AE.

Results in persistent or significant disability/incapacity

- The term disability means a substantial disruption of a person's ability to conduct normal life functions.
- This definition is not intended to include experiences of relatively minor medical significance such as uncomplicated headache, nausea, vomiting, diarrhea, influenza, and accidental trauma (e.g. sprained ankle) which may interfere with or prevent everyday life functions but do not constitute a substantial disruption.

Is a congenital anomaly/birth defect

Other situations:

- Medical or scientific judgment should be exercised in deciding whether SAE reporting is appropriate in other situations such as important medical events that may not be immediately life-threatening or result in death or hospitalization but may jeopardize the participant or may require medical or surgical intervention to prevent one of the other outcomes listed in the above definition. These events should usually be considered serious.

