4.5. Safety Analyses

The safety analyses will be based on the Enrolled Analysis Set, unless otherwise specified.

Only the AEs/SAEs related to study procedures are collected in this study. If there are no AEs/SAEs in the database, a standard 'No data to report' display will be generated.

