4.5.2.1. Additional Safety Assessments

Routine safety assessments (e.g., ECG and vital signs) were only collected during screening. Other than the collection of AE information, no further safety assessments were mandated in the protocol after screening was complete. Therefore, no additional safety information will be summarised for this study.

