6.1.1. Participant Disposition

A summary of the number of participants in each of the participant level analysis set mentioned in Section 3 will be provided.

A summary of subject status and reason for study withdrawal will be provided. This display will show the number and percentage of subjects who withdrew from the study, including primary reasons for study withdrawal. The Enrolled Analysis set will be used.

A summary and listing of screening status and reasons for screen failure will be provided using the Screened Analysis Set. Per GSK reporting standards, participants who were rescreened will appear once in these displays according to their final status.

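### No visible SAP display reports all-cause deaths, although the protocol requires death data for every death

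*SAP*

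**What the plan says.** **Collection.** Protocol 7.5.6: "For all deaths, whether or not they are considered SAEs, specific Death sections of the CRF will be required to be completed". Protocol Table 2 schedules survival follow-up and vital signs every 26 weeks to week 104. Survival follow-up applies to participants who do not enter a treatment protocol.

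**Definition.** Protocol 9.3.2 says that an event which is not an AE cannot be an SAE, and gives "death due to progression of disease" as an example.

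**Reporting.** SAP 4.5.2 plans the following: "A summary of fatal SAEs will also be provided"; "A Summary of Fatal AEs and Non-serious AEs by SOC and PT will also be provided"; and a listing of fatal SAEs. On the source of these outputs, SAP 4.5 states: "Only the AEs/SAEs related to study procedures are collected in this study". SAP 4.5.2.1 argues that routine safety assessments were confined to screening and that only AE information was required afterwards, and concludes: "Therefore, no additional safety information will be summarised for this study".

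**Nearby text.** SAP 6.1.1 plans a disposition display: "A summary of subject status and reason for study withdrawal will be provided". It does not name death as a category. SAP 4.7 declares no change from the analyses planned in protocol amendment 3.

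**The concern.** The cohort has advanced or metastatic solid tumours, and part of it may be followed for two years. Deaths from progression are to be expected, and the protocol makes their recording mandatory. The visible safety displays draw only on the AE data, from which expected-progression deaths are removed by definition.

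Two things are at stake. First, a reader of the synoptic CSR may take the fatal AE/SAE tables as the mortality of the cohort, which they are not. Second, protocol 2.3.1 names specimen acquisition as the primary risk to patients. Under Table 2 a repeat biopsy may be taken at progression, which is when a death soon afterwards is most easily put down to the disease. Once a site judges it so, the death drops out of the fatal tables. The tables then cannot test the judgement on which they depend.

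**Working it through.** The documents state no expected number of deaths, so there is no plan figure to reproduce. The check is a trace through the text, followed by a scale calculation.

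**1. Which deaths can reach the fatal AE/SAE outputs?** The answer depends on which statement of collection scope applied.

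| Source | Events collected | Unrelated, non-progression death | Expected-progression death |
|---|---|---|---|
| SAP 4.5 | procedure-related only | excluded | excluded |
| Protocol SoA, Table 1 footnote: "SAEs assessed as related to study procedure(s) or lead to study withdrawal" | related, or leading to withdrawal | may enter | excluded |
| Protocol 7.5.1 | all SAEs at SoA time points | may enter | excluded |

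The three statements disagree on the third column and agree on the last, because Appendix 3 applies to all of them.

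**2. Is the premise of SAP 4.5.2.1 correct?** Protocol 7.5.6 requires Death CRF sections throughout, and Table 2 requires vital signs and survival follow-up to week 104. The premise does not match the protocol.

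**3. Scale of procedure-related deaths.** Protocol 2.3.1 cites a pan-tumour study with 4,627 patients and no biopsy-related deaths.
- One-sided 95% upper limit: 1 − 0.05^(1/4627) = 0.000647, or 0.065%. Times 400 participants = 0.26 deaths.
- Two-sided 95% upper limit: 1 − 0.025^(1/4627) = 0.000797, or 0.080%. Times 400 = 0.32 deaths. P(at least one) = 1 − (1 − 0.000797)^400 = 0.27.

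This applies the limit to all 400. Archival tissue is the default in protocol 5.1, so fewer will have a study biopsy.

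**4. Scale of all-cause deaths.** The documents give no survival rate. Assume exponential survival and complete 24-month follow-up, so the proportion dead is 1 − 2^(−24/median).

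| Assumed median (months) | Dead by 24 months | Per 100 followed |
|---|---|---|
| 9 | 84% | 84 |
| 12 | 75% | 75 |
| 18 | 60% | 60 |
| 24 | 50% | 50 |
| 36 | 37% | 37 |

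The result is given per 100 because the number entering Table 2 follow-up is not stated. Withdrawal or early study closure would lower it. Steps 3 and 4 also have different denominators: all enrolled participants in one, and those followed without entering a treatment protocol in the other. They show that the two kinds of death can differ greatly in number. They do not estimate what the report will omit.

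**The case against.** **Removed text.** SAP numbering passes from 4.3 to 4.5, and objectives are redacted. Amendment 02 added an objective on summarising safety data that is not in the visible list. A reader might infer that the fatal AE/SAE outputs are the only death outputs in the whole SAP. The documents cannot establish that, so the point is confined to visible displays.

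**Disposition.** The subject-status and withdrawal-reason summary could count deaths. A reader might infer that the report will show almost none; that is not supported. The limit that stands is that no death category, cause or timing from a procedure is planned there.

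**AE scope.** On the protocol's wording, deaths that are neither procedure-related nor due to progression may appear in the fatal tables. This stands. The fatal tables therefore cannot safely be called procedure-related until the scope is settled.

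**Misattribution.** Appendix 3 keeps events more severe than expected as AEs. A fatal biopsy complication recognised as such is an SAE, recorded from consent, with a causality assessment and any postmortem findings supplied. Only a wrong attribution to expected progression hides it. Fresh biopsies may also be few. This limits how often the problem can arise. It does not supply a check that is independent of attribution.

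**Proportion.** This is a descriptive study without investigational product, reported in a synoptic CSR, and protocol 8.4.1 plans AE summaries only. That argues for a small remedy. It does not explain why mandatory death data reach no visible display, and the reason SAP 4.5.2.1 gives for stopping is contradicted by the protocol.

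**Conclusion.** The point holds in a limited form. The protocol requires death data for every death, and no visible SAP display reports them. The fatal AE/SAE outputs exclude deaths judged to be expected progression on every reading of the collection scope, so they are not mortality and cannot check attribution after a biopsy. The stated reason for planning no further safety summaries conflicts with protocol 7.5.6 and Table 2.

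The number of deaths left out is unknown. The illustrative 37 to 84 per 100 followed rests on assumed medians of 36 down to 9 months, exponential survival and full 24-month follow-up. It cannot be scaled to 400, because survival follow-up covers only participants who do not enter a treatment protocol, and those who consent to a GSK treatment protocol complete this study at that point (protocol 4.2). No figure in the documents is wrong on this point. It is an inexpensive improvement to reporting and does not invalidate the study.

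**What to change.** 1. Add to SAP 4.5.2 one all-cause deaths summary and one participant-level listing from the Death CRF, on the Enrolled set. Show cause as recorded, days from enrolment, and days from the last study procedure or biopsy, whatever the attribution.
2. Correct the premise in SAP 4.5.2.1 so that it acknowledges the Death CRF and the Table 2 assessments.
3. Reconcile SAP 4.5 with the protocol SoA and protocol 7.5.1 on which AEs and SAEs were collected.
4. Footnote the fatal AE/SAE tables with the actual collection scope and the progression exclusion. Do not retitle them as procedure-related, which would mislabel them if the protocol's wider scope was followed.

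If redacted text already contains an all-cause deaths display, a cross-reference from 4.5.2 may replace item 1, provided that it gives timing from the last procedure. If the display is deliberately omitted, say so in SAP 4.7.

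**Cost.** A minor revision of the approved SAP, with one extra table and one extra listing. Collection of death data is already required, so item 1 needs no protocol amendment. Protocol 7.5.6 does not describe the content of the Death CRF, so confirm that cause and date are recorded before fixing the layout.

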4.5.2.1. Additional Safety Assessments

Routine safety assessments (e.g., ECG and vital signs) were only collected during screening. Other than the collection of AE information, no further safety assessments were mandated in the protocol after screening was complete. Therefore, no additional safety information will be summarised for this study.

4.6. Interim Analyses

Due to the continuous nature of this study, there is no interim analysis phase. Data will be continuously monitored and analysed in real-time during the course of the study.

4.7. Changes to Protocol Defined Analyses

There were no changes or deviations to the originally planned statistical analysis specified in the protocol amendment 3 (Dated: 25-OCT-2021).

5. SAMPLE SIZE DETERMINATION

Since MDCI does not aim to test any specific hypothesis or answer any particular question, there is no statistical requirement to reach a specific number of samples and patients.

6. SUPPORTING DOCUMENTATION

6.1. Appendix 1 Study Population Analyses

Unless otherwise specified, the study population analyses will be based on the Enrolled Analysis Set.

6.1.1. Participant Disposition

A summary of the number of participants in each of the participant level analysis set mentioned in Section 3 will be provided.

A summary of subject status and reason for study withdrawal will be provided. This display will show the number and percentage of subjects who withdrew from the study, including primary reasons for study withdrawal. The Enrolled Analysis set will be used.

A summary and listing of screening status and reasons for screen failure will be provided using the Screened Analysis Set. Per GSK reporting standards, participants who were rescreened will appear once in these displays according to their final status.

6.1.2. Demographic and Baseline Characteristics

The demographic characteristics including age, gender, ethnicity, weight at screening and race will be summarized with descriptive statistics. In addition, the following age categories will be summarized: 18-64, 65-84 and >=85 based on the Enrolled Analysis Set.

A listing of demographic characteristics and race will be provided.

6.1.3. Protocol Deviations

Important protocol deviations will be summarized.

Protocol deviations will be tracked by the study team throughout the conduct of the study. These protocol deviations will be reviewed to identify those considered as important as follows:

- Data will be reviewed prior to freezing the database to ensure all important deviations (where possible without knowing the study intervention details) are captured and categorised in the protocol deviations dataset.
- o This dataset will be the basis for the summaries of important protocol deviations.

If there is no data to report a standard "no data to report" displays will be produced.

6.2. Appendix 2 Data Derivations Rule

6.2.1. Study Day and Reference Dates

The reference date is the study enrolment date and will be used to calculate study day

The study day is calculated as below:

- Assessment Date = Missing → Study Day = Missing
- Assessment Date < Reference Date → Study Day = Assessment Date Ref Date
- Assessment Data ≥ Reference Date → Study Day = Assessment Date Ref Date + 1

6.2.2. Assessment Window

No Assessment window will be applied.

6.2.3. Handling of Partial Dates

The partial date imputation will follow ADaM conventions. The ADaM approach is to populate the numeric date variables with the imputed date and add a flag variable to the dataset that indicates the level of imputation.

The flag variable can contain the values: blank, 'D', 'M', 'Y'.

blank: indicates that no imputation was done

D='Day': indicates that the day portion of the date is imputed

M='Month': indicates that the month and day portions of the date are imputed

Y='Year': indicates that the entire date (year, month, and day) is imputed

Example of date variables:

XYZD - character date variable

XYZDT - numeric date variable

XYZDTFL - flag variable

Details on imputing partial dates for specific datasets are outlined below

Element	Reporting Detail			
General	 Partial dates we displays. However, whe temporary var partial dates me specific analys. Imputed partial onset or duration. 	al dates will be displayed as captured in participant listing ays. ever, where necessary, display macros may impute dates as orary variables for sorting data in listings only. In addition, al dates may be imputed for 'slotting' data to study phases or for fic analysis purposes as outlined below. ted partial dates will not be used to derive study day, time to a or duration (e.g., time to onset or duration of adverse events), apsed time variables (e.g., time since diagnosis).		
Adverse Events	Partial dates for following con Missing start day	es for AE recorded in the CRF will be imputed using the conventions:		
	Missing start day and month	If study enrollment date is missing, then set start date = January 1. Else if study enrollment date is not missing:		

Element	Reporting Detail	
	Missing end day	A '28/29/30/31' will be used for the day (dependent on the month and year).
	Missing end day and month	No Imputation
	Completely missing	No imputation
	start/end date	

6.2.4. Early PK Access Key Activities

Not applicable.

